8.6.1 Sample Size Re-estimation

The sensitivity and specificity need to be estimated in an unbiased manner using the most accurate assumptions. This will be accomplished using an interim analysis after the first 800 subjects are evaluated by the independent readers; specific attention will be paid to the "internal control." The specificity will be the primary effectiveness endpoint and the sensitivity will be the secondary effectiveness endpoint for this sample size recalculation; the sample size will not be decreased under any circumstances. The final sample size of the Pivotal Study will be determined by an interim analysis after the first 800 subjects have been evaluated with Imagio relative to the results of any pre-scheduled biopsies; the final sample size will depend on the numbers of masses biopsied, the percent of biopsied masses with a cancer diagnosis, and the sensitivities and specificities for Imagio and IUS. The interim analysis will be conducted once at least four of the seven registration readers complete the review of the 800 cases. The final sample size will not exceed 2,400 masses.

To preserve the Type I error, the observed specificity differences will not be used in the sample size reestimation and there will not be an interim stopping rule for the study.

8.7. Analyses

8.7.1 Sensitivity and Specificity

The specificity for Imagio relative to the Imagio ultrasound component (IUS) will be assessed using a one-sided 99.5% lower confidence bound. The goal is to establish at least a 6% absolute advantage in specificity for Imagio vs IUS.

Seno Clinical Study Protocol: PIONEER-01
300176 Rev 8 PIONEER 01 Protocol Amendment 3.2

The sensitivities and specificities will be displayed for Imagio relative to IUS; in these displays, the consequences of Imagio (positive vs. negative) will be considered and compared using a generalized linear model (GENMOD) to account for correlated outcomes among the readers.. Additional analyses will be performed using the nomograms for the POM and the diagnosis based on the five Imagio features. The first nomogram models the probability of malignancy (NPP) while the second nomogram models the probability of cancer (NPC). The sensitivity and specificity of the averaged prediction (NPP and NPC) being ≥ 0.1 or ≤ 0.1 will be evaluated. The ability of the nomogram to downgrade benign masses with IUS POM $\leq 30\%$ and CDU POM $\leq 30\%$ will also be assessed. The linear regression (NPP) and the logistic regression (NPC) models behind the predictions are based solely upon the Pilot Study data.

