The Pilot Study (Pilot Phase of the Pivotal Study) data will be used to validate the existing algorithm to a pre-determined diagnostic rule set based on OA image characteristics established in a previously conducted independent Feasibility Study. The Pilot Study will collect imaging data from 100 subjects passing Quality Assurance review conducted by three central radiologists blinded to clinical history and histopathology outcome. Then a pool of at least 20 other independent radiologists (readers) not affiliated with any sites will be prospectively trained and then tested for proficiency using the image sets constructed by the central radiologists using the last 70 of the 100 Pilot cases. The first 30 cases will be used to familiarize readers with the image sets, the viewing logistics, and the eCRF to be completed, prior to reader proficiency testing. Upon establishing and meeting prospective rules for proficiency (based on Imagio sensitivity [missing at most one cancer] and Imagio specificity ≥30% after excluding the first 30 cases to allow for learning), a subset of 7 proficient readers will be selected for purposes of reading IUS and Imagio OA and 3 other readers will be selected to share the reimbursement reads of multiple combinations of imaging modalities with or without Imagio, The registration readers will be selected at random based on availability and once all readers are tested for proficiency; reimbursement readers will be selected by the Seno Medical Director. All registration readers will be proficiency tested and selected prior to making any Pivotal Study i.e., reads for subjects 101 and beyond, which will constitute the Pivotal Study. All effectiveness analyses will be conducted at the mass-level; it is projected that no more than 5% of all subjects will have multiple masses. A minimum of 100 Pilot Study masses and at least 1,700 Pivotal Study masses passing QA review and excluding enrollment failures are to be included. Enrollment will continue until there are 100 Pilot Study masses and at least 1,700 Pivotal Study masses that pass both criteria. The 100 Pilot Study cases will be used for education, training, and publication purposes; only the Pivotal Study cases will be used to support Imagio registration for this indication for use. All selected registration readers will evaluate all masses according to a MRMC design. To mimic the real world setting as closely as possible, all readers will receive feedback on the histopathology results in read only mode following their case reads after completing their locked evaluations; readers may not change results after receiving feedback. For the Pivotal Study, subsets of 5% of registration image sets and 2.5% of all reimbursement image sets will be reread to assess learning and consistency; the first reads will be used in the data analyses for registration and reimbursement. The PMA filing will be based

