A multi-stage process is implemented to establish reader proficiency and to select independent readers using Feasibility Study data, Validation and Verification Study data, and the Pilot Study data. The Pilot Study (Pilot Phase of the Pivotal Study) data are used to confirm the acceptability of the existing algorithm to be evaluated according to a pre-determined diagnostic rule set based on OA image characteristics (established in the previously conducted Feasibility Study). The Pilot Study collects imaging data from 100 subjects passing Quality Assurance review conducted by three central radiologists under the direction of the ICC. A pool of at least 20 other independent radiologists not affiliated with the ICC or any sites will be prospectively trained by the Seno Medical Director through face-to-face and webinar lectures as well as through reading practice sessions. All such trained readers are then screened by Seno for willingness to cooperate and ability to understand opto-acoustics. Equipment is then installed in their preferred reading environment and reading software is loaded for conducting further practice sessions. These readers are then tested for proficiency using the image sets constructed by the central radiologists using the last 70 of the 100 Pilot cases; the first 30 cases are not be used in order to let individual readers get familiar with the image sets, the viewing logistics, and the eCRF to be completed. Readers are not given a second chance to establish proficiency unless the pool of proficient readers is depleted due to reader dropouts.

Upon establishing and meeting prospective rules for proficiency (based on Imagio sensitivity [missing at most one cancer] and Imagio specificity ≥30% after excluding the first 30 cases to allow for learning), a subset of 7 proficient readers are selected for registration reads (IUS and Imagio) and 3 other readers are selected for reimbursement. The registration readers are selected among those meeting the proficiency standard; reimbursement readers are selected by the Seno Medical Director.

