8.7.5 BI-RADS Analyses

Results will be displayed according to the BI-RADS classification to provide insight into currently used guidelines. The matched pairs cross tabulation of Imagio versus its' ultrasound component will be assessed.

The ability of Imagio to downgrade BI-RADS 4a and 4b (or BI-RADS 3) relative to IUS and separately according to the site investigator to BI-RADS 3 (or BI-RADS 1-2) for the benign cases and to then symmetrically upgrade BI-RADS 3, 4a, 4b, and 4c according to Imagio relative to IUS and separately relative to the site investigator for the cancer cases; the discordant pairs will be compared using a McNemar's test for individual readers and a generalized linear model for grouping readers. In addition, the ability of Imagio to improve the site investigator classification for the BI-RADS 4ab (or BI-RADS 3) subgroup will be assessed separately for the cancer and benign cases; the percents (Imagio positive vs. Imagio negative) will be separately evaluated using a two-sided Fisher Exact Test.

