8.7.7 Other Analyses

The sensitivity and specificity for Imagio and the Imagio ultrasound component will be generated for individual readers. The learning curve of individual readers will also be assessed in units of at least 100 cancers and at least 200 benigns to check if sensitivities and specificities improve as more cases are read.

Inter-reader variation will be evaluated separately for cancer cases and for benign cases for the readers. Inter-reader variability for these two subsets (cancers, benigns) will be analyzed using an ANOVA model where the readers are considered to be fixed effects; a random effects model will also be run. Intra-reader variation will be evaluated using paired t-tests applied to the paired POMs, and BI-RADS separately for cancer cases and for benign cases.

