9.12 Data Generation and Analysis

Data will be collected in accordance with Title 21 CFR Part 11 and will be analyzed in accordance to a prospective statistical analysis plan developed in accordance with the statistical section of this protocol and the latest FDA guidance documents for imaging modalities.

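### Section 8.1.1 treats every lesion as independent although a woman may contribute up to three, and the only pooled-reader model named supports conclusions for the seven readers alone unless readers are made random

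*Protocol*

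**What the plan says.** Section 8.1.1 declares a multi-reader, multi-case (MRMC) design with seven registration readers, and the synopsis adds: "All selected registration readers will evaluate all masses according to a MRMC design". Effectiveness is analysed by mass. Section 8.1.1 gives as the reason that some women will have more than one mass biopsied, and it allows up to three per woman across both breasts. It then expects at most 5% of women to have several masses, concludes that no repeated measures analysis is needed, and lays down that lesions count as independent.

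For Hypothesis 1, section 8.7.1 says the specificity of Imagio relative to IUS "will be assessed using a one-sided 99.5% lower confidence bound". Section 8.1.1 sets the same one-sided 99.5% level for non-inferiority (Hypothesis 2). The next paragraph of 8.7.1 says the displayed sensitivities and specificities are "compared using a generalized linear model (GENMOD) to account for correlated outcomes among the readers", and 8.7.5 again uses "a generalized linear model for grouping readers". No other pooled-reader model is named for these comparisons. Random readers appear only in section 8.7.7, where inter-reader variation is examined "using an ANOVA model where the readers are considered to be fixed effects; a random effects model will also be run".

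On how the seven are chosen, the synopsis says "The registration readers will be selected at random based on availability", and section 3.2 says "The registration readers are selected among those meeting the proficiency standard".

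**The concern.** Two masses in one woman share breast tissue, operator, device session and acquisition quality, so the Imagio-minus-IUS differences on them may be correlated. A rule that ignores this understates the variance of both registration bounds. The protocol states the rule outright, so it is not a detail left for later.

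The second source of dependence is the reader. An MRMC comparison varies over cases and over readers. A GENMOD repeated structure handles one clustering factor. With the case as the cluster, it accounts for seven readers scoring the same mass but leaves out the variation in how much different readers gain from Imagio. Such a bound is correct for the average of these seven readers. It holds its 0.5% level for other readers only if readers do not differ in that gain. The readers come from a larger proficient pool, yet the protocol does not say which conclusion it wants.

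**Working it through.** **The plan's own figure.** Table 6 gives 860 benign masses (0.5% level, 6-point difference, 20% discordant, 90% power). The McNemar formula, one-sided, gives

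n = (2.576·√0.20 + 1.282·√(0.20 − 0.06²))² / 0.06² = 822,

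or 839 with a continuity correction; exact power at 860 is 90.8%. Table 6 is therefore reproduced to within 2.5% by a formula with one independent pair per mass, and with no term for the woman or the reader.

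**Lesion independence.** Inputs: 5% of women with several masses and at most three masses each (both 8.1.1). The within-woman correlation of the paired difference (ICC) is not in the documents; 0.5 is assumed, with a range of 0.2 to 0.8. With m masses per woman, the design effect is 1 + ICC·Σm(m−1)/Σm.

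- Two masses each: Σm(m−1)/Σm = 0.10/1.05 = 0.095, so the design effect at ICC 0.5 is 1.048.
- Three masses each: 0.30/1.10 = 0.273, so it is 1.136.

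The true one-sided error of a nominal 0.5% bound is 1 − Φ(2.576/√design effect): 0.59% and 0.78%. Over ICC 0.2 to 0.8 it runs from 0.5 to 1.0%. At ICC 0.5, 1,000 benign masses carry the information of 1,000/1.048 = 955 or 1,000/1.136 = 880, both still above 860.

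**Readers.** Assumed, because the documents give neither: the SD between readers of the true Imagio-minus-IUS difference (τ), and the between-reader correlation of the paired differences on the same mass (r, 0.2 to 1.0). With seven readers, variance v per paired difference and n masses:

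- variance seen by a case-clustered model: Vc = (v/n)(1 + 6r)/7
- omitted reader variance: Vr = τ²/7
- error for other readers: 1 − Φ(2.576·√(Vc/(Vc + Vr)))

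Hypothesis 1 uses v = 0.20 and n = 1,000. Worked case, τ = 2 points and r = 0.2: Vc = 0.0002 × 2.2/7 = 0.0000629; Vr = 0.0004/7 = 0.0000571; √0.524 = 0.724; error 3.1%. Hypothesis 2 uses n = 420 and v = 0.08 − 0.05² = 0.0775. Table 7's 5% discordance cannot sensibly be used at the −5-point margin, since every discordant pair would then have to go against Imagio, so 8% is assumed.

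| τ (points) | Hypothesis 1 error | Hypothesis 2 error |
|---|---|---|
| 0 | 0.5% | 0.5% |
| 1 | 0.6–1.0% | 0.7–1.1% |
| 2 | 1.2–3.1% | 1.2–3.4% |

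At 12% discordant, the Hypothesis 2 range at τ = 2 is 1.0 to 2.3%.

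**Price of random readers.** At τ = 2 the Hypothesis 1 standard error grows by √(1 + Vr/Vc) − 1, which is 13% at r = 1.0 and 38% at r = 0.2. Power below is from a noncentral t with Satterthwaite-type degrees of freedom (Hypothesis 1: 6-point gain, 1,000 masses; Hypothesis 2: no true difference, 5% discordant, 420 cancers).

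| | r = 0.3 | r near 1 |
|---|---|---|
| Hypothesis 1, τ = 2 | 98% | about 87% |
| Hypothesis 1, τ = 3 | 84% | 73% |
| Hypothesis 2, τ = 2 | 96% | 86% |
| Hypothesis 2, τ = 3 | 70% | 64% |

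**The case against.** The cluster, the status of readers and the degrees of freedom are usual content of a statistical analysis plan, which is not shown. Section 8.7.1 attaches GENMOD to the displays and does not say that it produces the 99.5% bound. Section 9.12 promises a "prospective statistical analysis plan developed in accordance with the statistical section of this protocol", but adds current FDA imaging guidance, so a random-reader analysis is not excluded. This stands: a reader might infer that the protocol has fixed a fixed-reader bound for Hypotheses 1 and 2, and it has not.

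A reader might also infer that GENMOD could be clustered on the reader, with only seven clusters. The stated purpose, to handle correlation among readers' outcomes, points to the case as the cluster, so that reading has no support in the text.

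The target population is also open. No section claims generalisation beyond the seven, and the pool was trained, screened and tested by the sponsor, so a random-reader model would reach that pool at most. Shared training and rule sets may keep τ near 0 or 1, where the inflation is slight. This stands too, and is why stating the limit is an acceptable remedy.

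On lesions, 8.1.1 gives its reason (at most 5% of women), and 6.2.2 restricts follow-up to one mass when several are found and not recommended for biopsy. Two masses also affect the same bound only if both are benign or both malignant. These facts keep the effect small but do not justify the rule, because clustering on the subject costs almost nothing.

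**Conclusion.** The independence rule is stated, conflicts with the acknowledged multiple masses, and makes both registration bounds slightly too narrow: about 0.6 to 0.8% instead of 0.5%, given 5% of women with two or three masses and an assumed ICC of 0.5. It does not threaten the study's size.

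The reader point is secondary and conditional. Case-clustered GENMOD with readers not random is valid for these seven readers. Its Hypothesis 1 error for other readers would be about 0.6 to 3% for assumed reader SDs of 1 to 2 points, and 0.5% if readers do not differ. The documents supply no reader variance, so the true value is unknown. Taken together this is an improvement worth considering, not a flaw that undermines the registration comparisons.

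**What to change.** - **Section 8.1.1:** delete the statement that lesions are independent and the exclusion of repeated measures. Make the subject the cluster in GENMOD, which then covers both several masses in one woman and several readers on one case.
- **Section 8.7.1:** choose one of two statements. Either the 99.5% bounds for Hypotheses 1 and 2 rest on an MRMC variance with readers and cases both random and degrees of freedom suited to seven readers (for example Obuchowski-Rockette, with whole subjects as the cases), GENMOD being supportive; or the conclusions apply to these seven readers.

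Neither change needs new data; both are wording and programming. The price of the first option is a wider interval. If readers differ by about 3 points, power can fall below the 80% of section 8.1.1 and the 90% of Tables 6 and 7. The reader term τ²/7 does not shrink as masses are added, so in that case more masses alone would not restore it. The sponsor should weigh this before choosing.

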8.7.2 Histologic Considerations

The nature of the malignancies will be analyzed. While DCIS is considered malignant, many of the vascular and metabolic changes that might be detectable with OA may be limited to invasive carcinoma. Thus, the degree of invasive malignant and non-invasive (DCIS) malignant masses will be analyzed separately. It may be that OA is very effective in detecting invasive malignancy, but not as effective at detecting DCIS. The malignant potential becomes a consideration with OA risk benefit if it performed better for more invasive and more extensive malignancies, while a missed DCIS carries reduced risk. Other lower risk masses would include atypical ductal hyperplasia, atypical lobular hyperplasia, lobular carcinoma in situ, and lobular neoplasia which will be considered benign for the purposes of this study.

High risk masses will also be considered from the perspective of where to distinguish between benign and malignant disease. Specifically, histopathologic diagnoses of atypical ductal hyperplasia, atypical lobular neoplasia, and lobular carcinoma in situ, etc. are considered "in between" benign and malignant. These cases will be considered high risk as confirmed by the central pathologist. Since the features of high risk masses are nonspecific, usually reflecting the features of the underlying benign mass in which they arose, including such masses in the malignant category would reduce sensitivity. As a practical matter, such diagnoses are almost always require re-biopsy, e.g. a surgical excision, which often results in an upgrade to DCIS or invasive cancer. This information will be collected and included in the malignant category if so classified by the independent pathologist who will make the final determination. However, some cases, even after excision, may remain high risk so high risk masses will always be analyzed separately.

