Variable referral patterns across sites are expected. The referral pattern also varies depending on study site (academic vs. private practice), age, risk factors (family history of breast cancer, obesity), and breast BI-RADS density. Note that pre-screening and referral patterns influence diagnostic performance, helping to explain a breast cancer detection rate (BCDR) ranging between 18% and 40%. Endpoints of family history of breast cancer and obesity were not collected in this study.

The histologic findings of the biopsy procedure will serve as a gold standard for Imagio and the decision to not recommend a biopsy during the first 12 months will be regarded as evidence no of disease (True-Negative) for those not recommended for biopsy. Images will be assessed according to if the biopsy was performed immediately, delayed, or irrespective of timing through the 12 month follow-up interval.

High risk histologies will be analyzed separately from benign and malignant histologies in all data analyses. This reflects current practices where high risk masses are considered to be benign histologies but are always removed.

In general, superiority will be assessed using a two-sided 99% lower bound \geq 0 while non-inferiority will be assessed using a one-sided 99.5% lower bound greater than or equal to the non-inferiority margin.

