8.3. Analysis Populations

Seno Clinical Study Protocol: PIONEER-01
300176 Rev 8 PIONEER 01 Protocol Amendment 3.2

Confidential Page 54 of 80

All analyses will be performed with the intention to diagnose (ITD) study population which consists of all subjects coming in for their scheduled Imagio evaluation, having Imagio data declared evaluable, and having a biopsyat 12 months, or declared to be TN (or FP) at 12months.

There will be Truth Panel review to identify mass-specific subgroups and TN outcomes as well as reader-specific exclusions for the following:

- 1. Cases with QAR concerns (including cases with previously unidentified suspicious masses and cases where the Imagio evaluation was incomplete, unreliable, or unusable) for exclusions
- 2. Cases where the number or numbering of suspicious masses is under dispute (per QARs or IRs) for exclusions
- 3. Cases with questionable eligibility for exclusions
- 4. Cases with high risk histologies for separate analyses
- 5. Cases where individual IRs identified problems with specific image sets for exclusions
- 6. Cases with NDUs to determine if a mass was a True-Negative (TN) for specificity calculations.

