8.4. Demographics and Baseline Characteristics

The age, race, ethnicity, menopausal status, breast density, and BI-RADS score will be presented using descriptive statistics for the overall ITD population, by study population type, by sites (individual, private practice, academic), by biopsy status (immediate, delayed, never), and by cancer status (benign, high risk, malignant).

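### The protocol gives two answers on whether masses that remain high risk belong in the specificity denominator, and the 2x2 table in 8.5 settles neither

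*Protocol*

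**What the plan says.** Two paragraphs of Protocol 8.7.2 classify overlapping diagnoses. The first names atypical ductal hyperplasia (ADH) and atypical lobular hyperplasia, then "lobular carcinoma in situ, and lobular neoplasia which will be considered benign for the purposes of this study". The second begins "Specifically, histopathologic diagnoses of atypical ductal hyperplasia, atypical lobular neoplasia, and lobular carcinoma in situ, etc. are considered" and places these diagnoses between benign and malignant. It labels them high risk on confirmation by the central pathologist, sends those upgraded by the pathologist to malignant, and ends "so high risk masses will always be analyzed separately". ADH and lobular carcinoma in situ (LCIS) are named in both paragraphs.

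Section 8.1.1 states "High risk histologies will be analyzed separately from benign and malignant histologies in all data analyses". Its next sentence explains that in current practice "high risk masses are considered to be benign histologies but are always removed". Section 8.3 lists "Cases with high risk histologies for separate analyses" among the matters for Truth Panel review. Section 8.4 breaks down the baseline tables "by cancer status (benign, high risk, malignant".

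Section 8.5 defines specificity as TN/(TN+FP) from a table with a Cancer and a Benign column. Its assignment rules cover a cancer biopsy, a benign biopsy, no biopsy, and an unusable Imagio scan. None covers a high-risk result.

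**The concern.** Specificity at the 2% probability-of-malignancy threshold is the primary endpoint, and the Benign column is its denominator. For masses that remain high risk, one sentence puts them in that column, while another keeps them apart from benign in every analysis, which on its face includes H1 and H3. The same choice decides whether they count toward the 1,000 benign masses required in 3.1 and the 860 and 1,160 used in 8.6.

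The route to the label matters too. High-risk status is confirmed by the central pathologist. Under 5.7 the sponsor's Medical Director selects the cases for central review, and these may include lesions suspected of false positive or false negative opto-acoustic results. If high-risk masses leave the denominator, relabelling a suspected false positive removes it from specificity; if they stay benign, relabelling changes nothing. An open rule therefore interacts with case selection that can depend on the reading.

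**Working it through.** **Passages side by side, for a mass that remains high risk**

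| Section | What it implies |
|---|---|
| 8.7.2, first paragraph | Benign class |
| 8.7.2, second paragraph | High risk, always separate |
| 8.1.1 | Separate from benign and malignant in all analyses; next sentence notes that practice regards them as benign |
| 8.3 | Separate analyses, in a list where other items are marked for exclusion |
| 8.4 | Third status beside benign and malignant |
| 5.5 | Truth Panel reviews high-risk cases and records a benign-or-malignant classification |
| 8.5 | Cancer or Benign only; high risk not mentioned |

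**The plan's own figures reproduce**

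- Table 6 (6% difference d, 20% discordant η, 90% power, one-sided 0.5%): n = [2.576·√0.20 + 1.282·√(0.20 − 0.06²)]² / 0.06² ≈ 822, or 855 with a continuity correction, against 860 stated. Exact McNemar power at 860 is 90.8%.
- Table 8 (40% vs 45%, exact, one-sided 0.5%): at n = 1,160 the critical count is 508, so the observed specificity must reach 508/1,160 = 43.8%. Power is 80.4% against 80% stated.

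**Absolute specificity (H3)**

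Let h be the high-risk share of the column and p the proportion of those masses read positive. Neither is in the protocol. Take specificity of 45% without them, the Table 8 alternative. Then pooled specificity = (1 − h)·45% + h·(1 − p).

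- p = 55%, the same as other benign masses at 45% specificity: pooled = 45% for any h; shift 0.
- h = 3%, p = 70%: 43.65% + 0.90% = 44.55%; shift 0.45 points.
- h = 5%, p = 90%: 42.75% + 0.50% = 43.25%; shift 1.75 points.
- h = 10%, p = 90%: 40.5% + 1.0% = 41.5%; shift 3.5 points.

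The last two fall below 43.8%; the first two do not.

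**Paired difference (H1)**

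If the difference is 6 points in the other benign masses and, by assumption, Imagio gains nothing in the high-risk ones, the pooled difference is (1 − h)·6: 5.9, 5.7 and 5.4 points at h = 2%, 5% and 10%.

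**Counts and power if high-risk masses are counted as benign in accrual but then excluded**

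| Assumed h | 1,000 becomes | 860 becomes (H1 power) | 1,160 becomes (H3 power) |
|---|---|---|---|
| 0% | 1,000 | 860 (91.5%) | 1,160 (80.4%) |
| 2% | 980 | 843 (90.8%) | 1,136 (79.3%) |
| 5% | 950 | 817 (89.8%) | 1,102 (77.4%) |
| 10% | 900 | 774 (87.9%) | 1,044 (73.9%) |

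H1 power here is the normal approximation Φ[(d√n − 2.576√η)/√(η − d²)]; H3 power is exact binomial.

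**The case against.** The strongest reply is that the protocol already contains a workable rule: benign by class, plus a separate display. Section 5.5 has the Truth Panel review high-risk cases and record a two-way classification, which fits the two-column table. Section 8.3 marks several case types for exclusion but high-risk histologies only for separate analyses. Section 8.7.2 also analyses DCIS and invasive cancer separately, although both are malignant and 8.5 keeps both in the cancer group. The 8.1.1 sentence on current practice calls high-risk masses benign. This is the more natural reading, and it stands as a reason to choose retention. It does not override "High risk histologies will be analyzed separately from benign and malignant histologies in all data analyses", which makes no exception for the primary analysis. The sentence on practice is offered as the reason for that separation and assigns no column.

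Three stronger inferences are tempting and not supported:

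- That dropping these masses would raise specificity. This needs them to be read positive more often than other benign masses. Section 8.7.2 says instead that their features are nonspecific and usually those of the underlying benign lesion, which points toward little or no shift.
- That a shift of up to 3.5 points can be set against the 6-point H1 effect. H1 is a paired difference; including or excluding a mass does so for Imagio and IUS together.
- That the denominator will be chosen after results are known. Section 9.12 calls for a prospective analysis plan, which is not shown and may fix the rule. The protocol leaves room for such a choice; it does not show that one is intended.

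**Conclusion.** The point holds as an unresolved definition of the primary denominator. It is confined to masses that remain high risk; those upgraded to DCIS or invasive cancer go to malignant and are not in dispute. It does not show that specificity would be biased in a known direction.

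The effect is probably modest and cannot be fixed from the protocol. For absolute specificity, and so H3, it runs from zero to about 3.5 points, with the upper part resting on assumed values of 3-10% high risk and 70-90% read positive. Part of that range would cross the 43.8% that H3 needs. For H1, 6 points becomes about 5.9 to 5.4 under an assumed 2-10% share with no Imagio gain in those masses. Because it concerns the primary endpoint and labels that can come from selective review, it should be corrected before analysis.

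**What to change.** State one rule in 8.5. For example: masses that remain high risk after final pathology stay in the Benign column for H1 and H3 and count toward the benign accrual target; masses upgraded to DCIS or invasive cancer go to the Cancer column. This agrees with the two-column table and with 5.5 and 8.3.

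Reword 8.1.1 and the second paragraph of 8.7.2 so that separate analysis of high-risk masses means an additional display, and use one list of diagnoses in both paragraphs of 8.7.2. Pre-specify a sensitivity analysis of H1 and H3 that excludes these masses.

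The cost is wording and one extra table. Specificity may come out slightly less favourable than under exclusion.
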